#### For Patients with Measurable Disease (i.e., Target Disease)

Target Lesions	Non-Target Lesions	New Lesions*	Best Overall Response	Remarks
CR	CR	No	CR	
CR	Non-CR/Non-PD***	No	PR	
CR	Not evaluated	No	PR	
PR	Non-PD***/not evaluated	No	PR	
SD	Non-PD***/not evaluated	No	SD	
PD	Any	Yes or No	PD	No prior SD, PR or CR
Any	PD**	Yes or No	PD***	
Any	Any	Yes	PD	

* See RECIST 1.1 guidelines for further details on what is evidence of a new lesion.
 
** In exceptional circumstances, unequivocal progression in non-target lesions may be accepted as disease progression.
 
*** PD in non-target lesions should not normally trump target lesion status. It must be representative of overall disease status change, not a single lesion increase. Please refer to the Evaluation of Non-Target Lesions – Progressive Disease section for further explanation.
 
NOTE: Patients with a global deterioration of health status requiring discontinuation of treatment without objective evidence of disease progression at that time should be reported as “symptomatic deterioration.” Every effort should be made to document the objective progression even after discontinuation of treatment.
 
CR = complete response; PR = partial response; SD = stable disease; PD = progressive disease
				

#### Duration of Response

##### Duration of Overall Response

The duration of overall response is measured from the time measurement criteria are met for CR or PR (whichever is first recorded) until the first date that recurrent or progressive disease is objectively documented (taking as reference for progressive disease the smallest measurements recorded since the treatment started).

The duration of overall CR is measured from the time measurement criteria are first met for CR until the first date that progressive disease is objectively documented.

---

### Duration of Stable Disease

Stable disease is measured from the start of the treatment until the criteria for progression are met, taking as reference the smallest measurements recorded since the treatment started, including the baseline measurements.

To be assigned a status of stable disease, measurements must have met the stable disease criteria at least once after study entry at a minimum interval of 12 weeks.

## 6.2 Patient-Reported Outcomes Endpoints

The patient-reported outcomes assessment for this protocol will measure overall HRQL, treatment-related toxicities, breast cancer-specific symptoms, and adherence to protocol therapy.

### 6.2.1 Overall HRQL

Overall HRQL will be measured using the Functional Assessment of Cancer Therapy – General (FACT-G). The FACT-G includes 27 items that assess physical, functional, social and emotional well-being. We will select individual items *a priori* from the FACT-G to assess nausea, diarrhea, other side effects and overall bother by treatment side effects based on differences in the side effects noted with arm A vs. arm B. This *a priori* approach has also been employed for ATAC and E1Z03 data analysis. Use of the FACT-G will allow us to assess for overall HRQL, while performing a relatively broad screen for other, potentially unanticipated symptoms related to the Exemestane + Entinostat combination. All items are rated on a 5-point Likert scale, from 0 to 4.

### 6.2.2 Treatment-related toxicities

PROs to assess fatigue and GI distress will be administered to measure treatment-related side effects.

6.2.2.1 PROMIS Fatigue: The PROMIS Fatigue is a 7-item short-form. Minimally important difference (MIDs) scores have been empirically derived for the PROMIS Fatigue short form^56 and use of the PROMIS fatigue short form will also allow us to compare this metastatic breast cancer sample to other cancers, non-cancer chronic illnesses, and general population norms. All items are rated on a 6-point Likert scale, from 0 to 5.

6.2.2.2 FAACT: The Functional Assessment of Anorexia/Cachexia Treatment (FAACT) subscale consists of 12 items focused on appetite and nausea. We will use the 12-item FAACT-additional concerns subscale to assess differences in nausea and anorexia. All items are rated on a 5-point Likert scale, from 0 to 4.

6.2.2.3 FACIT-Diarrhea: The 11-item Functional Assessment of Chronic Illness Therapy (FACIT)-Diarrhea subscale will be used to assess diarrhea. All items are rated on a 5-point Likert scale, from 0 to 4.

6.2.2.4 PRO-CTCAE: The NCI PRO-CTCAE library includes 78 items to quantify patient reports of AEs. We have selected 6 common treatment-related symptoms which will be measured using 13 PRO-CTCAE items: decreased appetite, diarrhea, nausea, vomiting, joint aches, and muscle aches. We have selected 2 additional symptoms (bruising, hiccups) that we anticipate to be similar between treatment arms for validation purposes. Hiccups will be measured using 2 PRO-CTCAE items.

6.2.3 Breast cancer-specific symptoms

8-items of the FACT-Breast Symptom Index were assessed by Yost et al among patients with metastatic breast cancer being treated on E1193. The 8-items includes items assessing fatigue, pain (general and pain in specific bodily areas), nausea, shortness of breath, worry about condition worsening, trouble meeting needs of family and content with QOL. We will use six of the eight items that we believe will focus on the most proximal changes to assess TTD (an important secondary endpoint). We will NOT use the following questions: “I worry that my condition will get worse” and “Because of my physical condition, I have trouble meeting the needs of my family” in assessing TTD but will collect these items for additional exploratory work. All items are rated on a 5-point Likert scale, from 0 to 4.

According to Yost et al, using distribution-based criteria, the minimally important differences for the 8-items above ranged from 1.5 to 2.5 points with a median of 2.2 points. Cross-sectional anchor-based criteria yielded similar estimates, with score differences between adjacent categories of performance status ratings of 2.8 and 3.2 points.

6.2.4 Adherence

The ECOG-ACRIN Medication Adherence Scale Modified from the Morisky Index will be administered to understand the reasons for non-adherence to protocol therapy. There will be one Medication Adherence Scale form completed for each agent (entinostat /placebo and exemestane). The Medication Adherence Scale measures the likelihood that a patient will take prescribed medications. The Medication Adherence Scale has been validated against medication pill count methods of assessing compliance and used in a variety of settings. It is an 8-item measure with a Likert response scale. The minimal detectable change has been defined as 1.98 points (Muntner).

Patient’s adherence to protocol therapy will be quantified using the pill count (entinostat/placebo) and diary (exemestane) methods. Patients will be instructed to bring their medication bottles and diaries to clinic visits. Clinic or pharmacy staff will count the number of remaining entinostat/placebo pills or note the number of exemestane pills as taken on the pill diary, and will calculate the number of pills taken using a treatment form.

Rev. Add5  
Rev. Add7

Rev.4/15  
Rev.10/15  
Rev. 10/16  
Rev. Add5

## 7. Study Parameters

1. Baseline evaluations within 4 weeks prior to randomization unless specified.
2. Prestudy scans and x-rays used to assess all measurable or non-measurable sites of disease must be done  $\leq$  4 weeks prior to randomization.
3. Prestudy CBC (with differential and platelet count) and all required prestudy chemistries must be done  $\leq$  4 weeks before randomization, as outlined in Section [3](#).

	Baseline	Cycle 1 Day 15	End of Cycles 1 and 2	End of Cycle 3	End of each cycle (cycle 3-forward) 	Every 3 cycles (cycle 3, 6 etc)	At discontinuation of treatment 	Post treatment 
History, Physical Exam, ECOG PS, Vital signs, Height, Weight	X 		X	X	X		X	X
Symptom/Toxicity assessments	X 		X	X	X		X	
CBC 	X	X	X	X	X		X	
Chemistries 	X	X	X	X		X	X	
Serum estradiol 	X							
ECG	X							
Bone scan 	X			X		X		X 
Tumor assessment by CT or MRI 	X			X		X	X	X 
Serum or Urine Pregnancy Test 	X							
PRO Assessments 	X			X		X	X	X
PRO Assessment: FBSI 	X		X	X	X			
PRO-CTCAE 	X		X	X	X		X	
Exemestane 				X (daily)				
Entinostat/placebo 				X (weekly)				
LHRH agonist (pre/perimenopausal female and all male participants only) 				X (monthly)				
Pill Count/Diary 			X	X	X	X	X	
Concomitant Medications	X		X	X	X		X	X 
Biological Sample Submissions [See Sections 11 and 12 ]								
Whole blood, one (1) 8mL CPT citrate tube 	X	X						

	Baseline	Cycle 1 Day 15	End of Cycles 1 and 2	End of Cycle 3	End of each cycle (cycle 3-forward) 	Every 3 cycles (cycle 3, 6 etc)	At discontinuation of treatment 	Post treatment 
FFPE tumor tissue (primary & metastatic) 	X							
Whole blood, one (1) 8mL ACD yellow top 	X							

	Cycle 1, Day 1 [2 samples drawn at least 2 hours apart, 2-5 hours after dosing]	Cycle 1, Day 15 [1 sample drawn 1 hour after dosing]	Within 72 hours prior to the start of Cycle 2
Population Pharmacokinetics [OPTIONAL PER PATIENT CONSENT]: Plasma, one (1) 6mL K2EDTA lavender top tube per time point 	X	X	X

- Physical exam, ECOG PS, vital signs, and symptom/toxicity assessment must be performed ≤ 2 weeks before randomization.  
**NOTE:** Height measurements may have been taken > 4 weeks from baseline.
- CBCs, which includes WBC, ANC, Platelets, Hgb, and Hct required for protocol therapy must be done ≤ 72 hours prior to Cycle 2 and every cycle thereafter. Baseline CBCs do not need to be repeated prior to Cycle 1 Day 1.
- Albumin, alkaline phosphatase, total bilirubin, bicarbonate, BUN, calcium, chloride, creatinine, glucose, magnesium, phosphorus, potassium, total protein, SGOT (AST), SGPT (ALT), sodium must be done ≤ 72 hours prior to Cycles 2-4 and every 3 cycles thereafter. Baseline chemistries do not need to be repeated prior to Cycle 1 Day 1.
- Only required for women age < 55 years and with intact ovaries as described in Section [3.1](#).
- Baseline bone scan required in all patients.  
**NOTE:** If bone scan done ≤ 6 weeks prior to registration showed no evidence suggesting bone metastases and no clinical indication of skeletal pain or other evidence suggesting bone metastases, a repeat baseline bone scan is not required.
- CT of the chest and CT or MRI of abdomen/pelvis are required at baseline. Subsequent imaging for the subject should be conducted on the same scanner using the same acquisition and reconstruction parameters. Those tests required to follow known site(s) of disease must be repeated at the end of 12 weeks from randomization and then every 12 weeks (3 cycles) during treatment and according to the follow up schedule if off treatment, until first progression of disease. **NOTE:** All tumor assessment should be scheduled based on calendar time (every 12 weeks) and not cycle length. Image thickness (reconstructed) should be 5 mm or less for CT and MRI, and contiguous slices are preferred to those with intervening gaps. Consistent use of contrast agent, dose, and injection parameters (including time of image collection after contrast) are recommended. See Section [10](#) for additional details and submission instructions.  
**NOTE:** If the CT of the chest and CT or MRI of abdomen/pelvis done ≤ 6 weeks prior to randomization showed no evidence of disease in the area(s) and no clinical indication suggesting new metastases, full re-staging including all areas is not required; however, ensure that disease is evaluable per RECIST 1.1 requirements (Section [6](#)).
- Patient-Reported Outcomes to be assessed at the following time (see Section [5.6](#) for detailed instructions):

PROMIS Fatigue, FAACT, FACIT-D: Baseline (before Cycle 1 Day 1), end of Cycle 3, end of Cycle 6, end of Cycle 12, at end of protocol treatment, including treatment discontinuation for any reason (i.e., toxicity, progression, completion of protocol therapy) and 4 weeks after end of protocol treatment, including treatment discontinuation for any reason (i.e., toxicity, progression, completion of protocol therapy).

Rev. 10/16 The ECOG-ACRIN Medication Adherence Scale Modified from the Morisky Index: end of Cycle 3, end of Cycle 6, end of Cycle 12, and at  
Rev. Add7 end of protocol treatment, including treatment discontinuation for any reason (i.e. toxicity, progression, completion of protocol therapy).  
Please note there will be one Medication Adherence Scale form completed for each agent (entinostat/placebo and exemestane).

FACT-G: Baseline (before Cycle 1 Day 1), end of Cycle 3, end of Cycle 6, end of Cycle 12, and at end of protocol treatment, including treatment discontinuation for any reason (i.e. toxicity, progression, completion of protocol therapy).

8. The FBSI will be administered at baseline, end of each cycle for the first six months after randomization, and then at the end of Cycles 8, 10, and 12. After Cycle 12, the FBSI will be administered on the same schedule as Tumor assessments until disease progression.
9. Pill counts for entinostat/placebo and diaries for exemestane should be collected at the end of each cycle until discontinuation of study treatment.
10. Repeat any test not done  $\leq$  the prior 28 days.
11. Every 3 months if patient is  $< 2$  years from study entry, every 6 months if patient is 2-5 years from study entry, and annually if patient is  $>5$  years from study entry. No specific requirements if patient is more than 10 years from study entry.
12. Tumor assessments are to be done up to (and including) the assessment which shows first progression of disease. If patient discontinues treatment due to reasons other than disease progression, concomitant medication and tumor assessments should be performed until disease progression on the following schedule: Every 3 months if patient is  $< 2$  years from study entry, every 6 months if patient is 2-5 years from study entry, and annually if patient is  $>5$  years from study entry. No specific requirements if patient is more than 10 years from study entry.
13. Submit blood samples to the [name] Laboratory from patients who answer "Yes" to "I agree to participate in the laboratory research studies that are being done as part of this clinical trial." Baseline blood samples should be collected after randomization, prior to start of treatment on Day 1 (preferably within 2 days of Day 1). Day 15 blood samples should be collected prior to entinostat/placebo dose on that day.  
**NOTE:** Do not start treatment on Fridays as the baseline and day 15 blood collections cannot be shipped on Fridays.  
Submit optional blood and tissue samples for future research to the ECOG-ACRIN Central Biorepository and Pathology Facility (CBPF) from patients who answer "Yes" to "I agree to provide additional specimens for research."
- Rev. 10/16 14. All specimens submitted must be entered and tracked via the online ECOG-ACRIN Sample Tracking System (STS). The exact date and time of entinostat/placebo administration and of PK plasma sample collection must be entered into the STS.
- Rev. 10/16 15. Kits are available for blood collection and shipment. Kit order instructions are provided in Appendix VI. Kit orders will, on average, be delivered within 3 business days from time of order placement.
16. PRO-CTCAE items will be administered at Baseline, end of each Cycle, and at end of protocol treatment, including treatment discontinuation following the same schedule as trial Symptom/Toxicity assessments.
17. Concomitant Medications will be collected up to 90 days from the end of study treatment.
18. A complete cycle of treatment is defined as 28 days ( $\pm 3$  days) of once daily continuous treatment of exemestane in combination with entinostat/placebo. A new cycle start is defined as the first planned date of entinostat/placebo for the cycle.

Rev. 10/16  
Rev. 9/17

19. Pre/perimenopausal females must have commenced treatment with LHRH agonist at least 4 weeks prior to randomization. If patients have received alternative LHRHR agonist prior to study entry, they must switch to goserelin for the duration of the trial.
20. For all women of child bearing potential, must be done  $\leq$  2 weeks prior to randomization.
21. Kits are being provided for the collection and shipment of the plasma samples for the population pharmacokinetic studies. Process and submit the plasma samples to Covance Central Laboratory Services. See Section [11.4](#) for instructions. To obtain starter kits and the Site Laboratory Instruction Manual please Email or Fax Appendix IX E2112 Covance Site Information/Initial Kit Order Form to Syndax. Please note Covance requires ten (10) days to process the form and ship the initial kits.

Rev.10/15 **8. Drug Formulation and Procurement**

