## 5.6 Patient-Reported Outcomes Administration

A detailed description of the PRO measures to be administered has been included in Section [6.2](#).

- 5.6.1 PRO Instruments to be administered:
- 1) The Functional Assessment of Cancer Therapy–General (FACT-G); 27 items
  - 2) The PROMIS Fatigue 7-item Short Form
  - 3) The Functional Assessment of Anorexia/Cachexia Treatment (FAACT; 12 items)
  - 4) Functional Assessment of Chronic Illness Therapy-Diarrhea (FACIT-D; 11 items)
  - 5) FACT-Breast Symptom Index (FBSI; 8 items) – taken from 8-item FBSI outlined by Yost et al that has event-based anchor points
  - 6) Medication Adherence Scale

Rev. Add7

- 5.6.2 PRO-CTCAE items to be administered:  
Select PRO-CTCAE items (16 items) will be administered to measure patient reporting of AEs.

Rev.4/15

- 5.6.3 Patient-Reported Outcomes Assessment Schedule
- 5.6.3.1 Brief symptom index to evaluate TTD: we plan to use 6 items from the FBSI -- FACT Breast Symptom Index to detect symptom deterioration. These 6 items have been selected to focus on proximal change in symptoms. However, we will collect all 8 of the items from the FBSI 8 outlined by Yost et al. These items will be administered at the following times:
- 1) Baseline (before Cycle 1 Day 1)

- 
- 2) End of Every Cycle for Cycles 1-6
  - 3) End of Cycles 8, 10, and 12
  - 4) Then administered on the same schedule as tumor assessments until disease progression (Note, for FBSI there are not assessments planned at or post progression).
- 5.6.3.2 PRO measures of treatment toxicities (PROMIS Fatigue, FAACT, FACIT-D) will be administered at the following time points:
- 1) Baseline (before Cycle 1 Day 1)
  - 2) End of Cycle 3
  - 3) End of Cycle 6
  - 4) End of Cycle 12
  - 5) At end of protocol treatment, including treatment discontinuation for any reason (i.e. toxicity, progression, completion of protocol therapy)
  - 6) 4-weeks after end of protocol treatment, including treatment discontinuation for any reason (i.e. toxicity, progression, completion of protocol therapy).
- Rev. Add7 5.6.3.3 The ECOG-ACRIN Medication Adherence Scale Modified from the Morisky Index will be administered:
- 1) End of Cycle 3
  - 2) End of Cycle 6
  - 3) End of Cycle 12
  - 4) At end of protocol treatment, including treatment discontinuation for any reason (i.e. toxicity, progression, completion of protocol therapy)
- 5.6.3.4 Patient-reported HRQL will be assessed using the FACT-G and will be administered:

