PRO assessments at treatment discontinuation and 4 weeks post-treatment discontinuation for all participants regardless of the reason for treatment discontinuation (toxicity, progression) will provide valuable information on HRQL and symptom burden. As noted by Rini et al. HRQL can appear to improve overall as the trial progresses due to participant selection bias. Participants with poorer performance status, more aggressive disease, and greater treatment toxicities come off treatment earlier. We may observe a high rate of attrition due to progression of illness. Patients on EE are expected to remain on treatment longer than patients on EP due to anticipated benefit in PFS. To obtain an unbiased assessment of HRQL and treatment toxicities, PRO assessment at the end of treatment and a short period of time following end of treatment (4 weeks) for all participants is needed. Otherwise, PRO assessments only capture data on participants who remain on treatment and are likely to be healthier, therefore, presenting a biased source of data that will likely indicate that HRQL improves over time. In addition, the assessment 4 weeks post-end of treatment will evaluate whether entinostat-related symptoms resolve within 4 weeks. This design (retaining participants who discontinue treatment) has been employed with other PROs studies such as the side effect sub-study of MA.27.

Rev. Add7

A PRO measure of breast cancer-specific symptoms will be administered at baseline, and every 28-day cycle for the first six months after randomization, and then every two cycles between 6 months and 1 year. After 1 year, the FBSI will be administered on the same schedule as tumor assessments until disease progression. The FBSI will be administered more frequently to allow for an assessment of time to treatment deterioration (TTD), a critical secondary endpoint.

The PRO measure of adherence to therapy, the Medication Adherence Scale - , will be administered as outlined in Section [5.6.3](#) (before Cycle 4, 7, 13, and end of protocol therapy). With the exception of baseline, these assessment time points correspond with other study PRO.

The FBSI and Medication Adherence Scale include 8 and 8 items each and the anticipated time to complete the 16 items is roughly 5-6 minutes. Please note there will be one Medication Adherence Scale form completed for each agent (entinostat/placebo and exemestane).

Rev. Add7

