#### 9.3.3 Time to Treatment Deterioration (TTD)

Another secondary endpoint of the study is to evaluate time to treatment deterioration (TTD) of arm A vs. B. TTD is a composite endpoint and it captures toxicity (measured by symptom worsening), symptom worsening due to disease progression between radiological tumor assessments (provided symptoms are being assessed more frequently than the radiological disease assessments), radiological confirmed disease progression and death. TTD is defined as time

from randomization to radiological confirmed disease progression or death or worsening of symptoms, whichever occurs first. Disease progression is assessed per RECIST v1.1. Symptoms deterioration will be measured by 6 items from the 8-item FACT-Breast Symptom Index (FBSI). The 6 items (GP1, GP2, GP4, GF7, B1, P2, scored 0-24) were selected as being most clinically relative and most responsive to “proximal” change based from clinical deterioration. In addition, the other two items (GP3 or GE6) in the 8-item FBSI will be collected as well for explanatory analysis.

The selected 6 items capture both symptoms related to progressive breast cancer (fatigue, malaise, pain, shortness of breath, overall change in QOL) as well as symptoms related to entinostat (fatigue, nausea, overall change in QOL). According to Yost et al, the minimally important difference (median 2.2, range 1.5-2.5) and anchor-based criteria overlapped (PSR 2.8 and 3.2), and based on these criteria, 2-3 point changes in this 8-item FBSI survey can be interpreted as a MID. To be conservative, symptom deterioration is defined as two consecutive available decreases of at least 3 points from baseline using the 6-item FBSI in this trial, and the second visit time will be used as the time of symptom deterioration in this case, unless it is the final score, for which one decrease is sufficient.

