In order to fully capture the impact of toxicity and disease progression before radiological assessment on patient’s QOL, symptoms will be assessed every cycle for the first six months after randomization, every two cycles between 6 months and 1 year. It then will be assessed based on the same schedule for tumor assessments until disease progression. Since symptom change cannot be associated with protocol therapy if the patient never receives any treatment on protocol, the primary population for the TTD analysis will be the enrolled 360 patients for the PFS analysis who receive at least one dose of protocol therapy (i.e., all treated patients in the first 360 enrolled patients). TTD will not be evaluated on the additional 240 patients primarily enrolled for the OS endpoint.

Because we expect that the benefits from improving PFS (and thus less symptoms from disease) on arm A will outweigh any increase in toxicity from the addition of entinostat to exemestane (more symptoms from the treatment), we hypothesize that the combination arm (A) will have a significantly longer TTD than arm B. It is expected that symptom deterioration will occur before radiological confirmed disease progression or death for some patients. Hence, the median TTD should be shorter than the median PFS for the same patient population. To be conservative, we assume that the median TTD is 4 months for patients on arm B, similar with our estimate for PFS in these patients. Assuming 9 patients (9/180=5%) will not start protocol therapy in each arm, with 171 evaluable patients per arm, there is 88% power to detect a HR of 0.67 for arms A/B based on the log-rank test when the analysis is conducted 30 months after study activation (same time as the primary analysis of PFS), assuming a median TTD

of 6 months on arm A (i.e., 50% improvement in median TTD), with a 2.5% one-sided type I error rate.

Rev. Add5

9.4 Analysis Plan for Primary Endpoints, Objective Response, Toxicity and Time to Treatment Deterioration

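### The FBSI is not scheduled at treatment discontinuation, and calendar and text conflict on whether it continues after a non-progression stop, so TTD can miss toxicity-driven worsening

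*Combined protocol and SAP*

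**What the plan says.** **Calendar (Section 7).** The row "PRO Assessment: FBSI" is marked at baseline and at end-of-cycle visits. Its cells for treatment discontinuation and post treatment are blank. The general PRO row is marked in both of those columns, and the PRO-CTCAE row is marked at discontinuation.

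**Footnote 8 to that row.** The early schedule reads "The FBSI will be administered at baseline, end of each cycle for the first six months after randomization". Forms then fall due every second cycle, from Cycle 8 up to Cycle 12. For the period beyond the first year the footnote gives this rule: "After Cycle 12, the FBSI will be administered on the same schedule as Tumor assessments until disease progression".

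**Section 5.6.3.1.** The FBSI list follows the same cycles and contains no end-of-treatment item. Its only stated exclusion is that "for FBSI there are not assessments planned at or post progression". Sections 5.6.3.2 to 5.6.3.5, which cover all the other instruments, each list an assessment at the end of protocol treatment for any reason.

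**Section 5.6.3, rationale.** The protocol wants "PRO assessments at treatment discontinuation and 4 weeks post-treatment discontinuation for all participants regardless of the reason for treatment discontinuation". It argues that PROs taken only from patients still on treatment come from healthier patients and are biased.

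**Section 9.3.3.** "TTD is a composite endpoint and it captures toxicity (measured by symptom worsening", and it also captures progression and death. Symptoms are assessed "every cycle for the first six months after randomization, every two cycles between 6 months and 1 year", then with the tumor assessments until progression. Symptom deterioration requires two consecutive available scores at least 3 points below baseline; a single such drop suffices if it is the final score.

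**The concern.** The FBSI is the only symptom input to TTD, and it is the only PRO instrument without an end-of-treatment visit. A patient who stops mid-cycle for toxicity may therefore have a last score that predates the decline. If nothing is collected afterwards, that decline never becomes a TTD event, and the patient stays event-free until progression or death.

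TTD is there to show whether a PFS gain outweighs added toxicity (Sections 1.5 and 9.3.3). An omission that falls mainly on the more toxic arm would weaken the endpoint in just that role. The plan itself expects unequal toxicity: Section 9.3.2 powers the toxicity comparison on grade 3-4 rates of 24% on arm A and 10% on arm B.

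**Working it through.** **1. The plan's own figure.** Section 9.3.3 gives 88% power for HR 0.67 with 171 patients per arm, medians of 6 and 4 months, and one-sided 2.5%. Section 9.2.1 gives 24 months of accrual with no added follow-up, and Section 9.4 gives TTD similar follow-up to PFS. With exponential times and uniform accrual, the expected events per arm are n × [1 − (1 − e^(−24λ)) / (24λ)], where λ = ln 2 / median.

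- Arm A: 171 × [1 − 0.9375/2.7726] = 113.2
- Arm B: 171 × [1 − 0.9844/4.1589] = 130.5
- Total: 243.7 events
- z = (√243.7 / 2) × |ln 0.67| − 1.960 = 7.805 × 0.4005 − 1.960 = 1.166, so power is 87.8%

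The 88% is reproduced with a data cut at month 24. A cut at month 30 gives 298.8 events and 93.3%. The power statement is not in question.

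**2. The passages side by side, for a patient who stops before progression.**

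| Source | At discontinuation | After discontinuation |
|---|---|---|
| Calendar row | blank | blank |
| Section 5.6.3.1 list | not listed | until progression; excluded only at or after it |
| Footnote 8 | not mentioned | first six months counted from randomization; after Cycle 12, follows tumor assessments |
| Footnote 12 (tumor assessments) | – | "tumor assessments should be performed until disease progression on the following schedule", starting at every 3 months |
| Section 9.3.3 | not mentioned | cycle-based to 1 year, then with tumor assessments to progression |

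The link to tumor assessments begins only after Cycle 12. Before that, visits are named by cycle, and Section 5.1 defines a cycle as 28 days of treatment. A patient who stops in Cycle 2 has no defined end of Cycle 3. Under the plan's medians and ignoring censoring, the share with a TTD event by month 12 is 1 − 2^(−12/6) = 75% on arm A and 1 − 2^(−12/4) = 87.5% on arm B. Most of the endpoint thus falls in the ambiguous period.

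**3. What the TTD rule does with a mid-cycle toxicity stop.**

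- *The last form already shows a drop of at least 3 points and no later form exists.* The final-score rule counts it. Nothing is lost.
- *The last form predates the decline and the grid is followed.* There is no symptom event. The unobserved gap is up to about 28 days in the first six cycles and up to two cycles (56 days) from month 6 to month 12.
- *The text is followed.* A later form may show the drop, but it then needs confirmation unless it is the final score.

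**4. A bound, on assumed inputs.** The documents give no entinostat stop rates. Suppose a fraction of each arm stops for toxicity, at a time uniform on 0.5 to 4 months, with a qualifying decline at the stop. Other TTD times are exponential and accrual is uniform over 24 months. Captured means the TTD time is the earlier of the two times; missed means the toxicity time is ignored. Large-sample Cox HRs (200,000 per arm, cut at month 30):

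| Assumed stops, A/B | Medians 6 vs 4: captured | missed | Medians 4 vs 4: captured | missed |
|---|---|---|---|---|
| 5%/2% | 0.696 | 0.669 | 1.026 | 1.002 |
| 10%/3% | 0.725 | 0.666 | 1.060 | 1.006 |
| 20%/5% | 0.793 | 0.665 | 1.125 | 1.000 |

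At trial size (171 per arm, medians 6 vs 4, cut at month 24):

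| Assumed stops, A/B | None missed: HR (power) | Half missed: HR (power) | All missed: HR (power) |
|---|---|---|---|
| 5%/2% | 0.70 (81%) | – | 0.67 (88%) |
| 10%/3% | 0.73 (69%) | 0.70 (82%) | 0.66 (89%) |
| 20%/5% | 0.81 (40%) | 0.73 (68%) | 0.67 (88%) |

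The 0.79 and 0.81 for 20%/5% come from the two cut dates.

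**The case against.** A reader might infer from the blank cells that the FBSI ends with treatment and that TTD is therefore biased toward arm A. The documents do not support that.

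- Footnote 8, on the same row, and Sections 5.6.3 and 9.3.3 tie the FBSI to randomization and progression. The only stated exclusion is at or after progression, when the TTD event has already occurred. Section 5.6.4 allows mail and telephone completion when the form does not coincide with a visit.
- The final-score rule already counts one drop on the last form. During the first six cycles forms are due every 28 days, so the gap is at most about one cycle.
- The simulated hazard ratios compare complete capture with none. They assume that every toxicity stop carries a 3-point drop, although Table 5.4.1 includes hematologic and laboratory toxicities that need not move a symptom score. They also add toxicity events to medians that Section 9.3.3 gives for the whole composite, so toxicity is counted twice.
- TTD is a secondary endpoint, and the other PROs at discontinuation still record toxicity.

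All of this limits the size of the point. It leaves the missing discontinuation assessment, the conflict between grid and text, and the lack of a defined visit after a stop within the first 12 cycles. The 3-monthly off-treatment tumor visits would not fill that gap: Section 5.6.3 plans to test whether entinostat symptoms resolve within 4 weeks, so a later score could miss them.

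**Conclusion.** The point holds as a scheduling gap combined with an internal inconsistency. No FBSI is planned at discontinuation, and the documents conflict on whether it continues after a stop without progression. If sites follow the grid, and if toxicity stops are commoner on arm A, some toxicity-driven worsening will go uncounted and TTD will tilt toward arm A.

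An established bias of a given size should not be inferred. The documents supply no entinostat stop rates, and the share of declines missed is unknown. Shifts such as 0.73 to 0.66 rest on assumed rates and on every decline being missed, so they are an upper bound on those inputs. Missing half gives 0.70 in that scenario. The everolimus–exemestane trial described in Section 1.3 had permanent discontinuation for adverse reactions in 24% versus 5%; that concerns another drug and indicates scale only.

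The change is still worth making. It closes a plausible differential gap in an endpoint that Section 5.6.3 itself calls critical, at almost no cost.

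**What to change.** 1. Mark the FBSI in the calendar's discontinuation column, and add it to Section 5.6.3.1, for stops before progression.
2. Reconcile the calendar row with footnote 8 and Section 9.3.3. State that the FBSI continues on calendar time from randomization until progression, regardless of treatment status.
3. State in Section 9.3.3 how the two-consecutive-decrease and final-score rules apply to the discontinuation score. Once later forms follow, that score is no longer the final one and a drop would need confirmation, so a decline that resolves after stopping might not count. The plan should say whether that is intended.

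**Cost.** FACT-G is already completed at discontinuation. Section 9.6.1 lists GP2, GP3, GP4 and GF7 as FACT-G items, so at most 8 − 4 = 4 of the eight FBSI questions are new at that visit. Forms after discontinuation can use the mail and telephone route already in Section 5.6.4. The sponsor should also accept that fuller capture may make the TTD result less favourable to arm A.
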